#### 3.2 Exclusion Criteria

Patients meeting any of the following exclusion criteria will not be eligible to enter in the study:

3.2.1 Participants with clinically active or symptomatic interstitial lung disease or interstitial pneumonitis (i.e., affecting activities of daily living or requiring therapeutic intervention) and patients with history of clinically significant interstitial lung disease or radiation pneumonitis.

- 3.2.2 Patients with clinically symptomatic brain metastases or leptomeningeal disease. Patients may be on a stable dose of corticosteroids to control brain metastases if they have been on a stable dose for two weeks prior to study treatment and are clinically asymptomatic.
- 3.2.3 Patients who have had radiation to the lung fields within four weeks of starting treatment. For patients receiving palliative radiation to thoracic vertebrae, ribs or other sites where the radiation field includes the lungs, radiation must be completed at least two weeks before starting treatment. For all palliative radiation to all other sites, at least 7 days must have elapsed prior to starting to treatment. At least six months must have elapsed from radiation given with curative intent.
- 3.2.4 Patients who have had major surgery (e.g., intra-thoracic, intra-abdominal or intra-pelvic) within 2 weeks prior to starting study drug or who have not recovered from side effects of such procedure. Video-assisted thoracic surgery (VATS) and mediastinoscopy will not be counted as major surgery and patients can be enrolled in the study ≥1 week after the procedure.
- 3.2.5 Patients unable or unwilling to undergo a biopsy for research during the screening period, 2-3 weeks into the course of therapy and at the time of progression.
- 3.2.6 Patients with a second, clinically active, cancer. Patients with second cancers which have been treated with curative intent and/or are currently inactive are allowed.
- 3.2.7 Patients who have undergone a bone marrow or solid organ transplant.
- 3.2.8 Known history of human immunodeficiency virus (HIV) seropositivity (HIV testing is not mandatory).
- 3.2.9 Participants who are receiving any other investigational agents. Patients previously treated with investigational agents must complete a washout period of at least one week or five half-lives, whichever is longer, before starting treatment.
- 3.2.10 Patients receiving concomitant immunosuppressive agents or chronic corticosteroid use, except those on steroid to control brain metastases, those on topical or inhaled steroids, or steroids given via local injection.

- 3.2.11 Patients with clinically significant, uncontrolled cardiovascular disease, such as:
  - Unstable angina within 6 months prior to screening
  - Myocardial infarction within 6 months prior to screening
  - Patients with a history of documented congestive heart failure (New York Heart Association functional classification III-IV)
  - Peripheral vascular disease
  - Patients with uncontrolled hypertension defined as a Systolic Blood Pressure (SBP) ≥ 160 mm Hg and/or Diastolic Blood Pressure (DBP) ≥ 100 mm Hg, with or without anti-hypertensive medication. Initiation or adjustment of antihypertensive medication(s) is allowed prior to screening
  - Ventricular arrhythmias
  - Supraventricular and nodal arrhythmias not controlled with medication
  - Other cardiac arrhythmia not controlled with medication
  - Patients with corrected QT (QTc) ≥450 ms (male patients) or ≥460 ms (female patients) using Fridericia correction (QTcF) on the screening ECG
  - Patients with history of congenital long QT syndrome or history of torsade de pointes
- 3.2.12 History of allergic reactions attributed to compounds of similar chemical or biologic composition to EGF816 or gefitinib.
- 3.2.13 Participants receiving any medications or substances that are strong inhibitors or inducers of CYP3A4 are ineligible. Because the lists of these agents are constantly changing, it is important to regularly consult a frequently-updated list such as http://medicine.iupui.edu/clinpharm/ddis/table.aspx; medical reference texts such as the Physicians' Desk Reference may also provide this information. As part of the enrollment/informed consent procedures, the patient will be counseled on the risk of interactions with other agents, and what to do if new medications need to be prescribed or if the patient is considering a new over-the-counter medicine or herbal product.
- 3.2.14 Unable or unwilling to swallow tablets or capsules.
- 3.2.15 Uncontrolled intercurrent illness including, but not limited to, ongoing or active infection, symptomatic congestive heart failure, unstable angina pectoris, cardiac arrhythmia, or psychiatric illness/social situations that would limit compliance with study requirements
- 3.2.16 Pregnant women are excluded from this study because the effects of EGF816 and gefitinib on a developing fetus are unknown. Because there is an unknown but potential risk for adverse events in nursing infants secondary to treatment of the mother with EGF816 or gefitinib, breastfeeding should be discontinued if the mother is treated with EGF816 and gefitinib.

## 3.3 Inclusion of Women and Minorities

Both men and women of all races and ethnic groups are eligible for this trial.

## 4. **REGISTRATION PROCEDURES**

## 4.1 General Guidelines for DF/HCC Institutions

Institutions will register eligible participants in the Clinical Trials Management System (CTMS) OnCore. Registrations must occur prior to the initiation of protocol therapy. Any participant not registered to the protocol before protocol therapy begins will be considered ineligible and registration will be denied.

An investigator will confirm eligibility criteria and a member of the study team will complete the protocol-specific eligibility checklist.

Following registration, participants may begin protocol therapy. Issues that would cause treatment delays should be discussed with the Overall Principal Investigator (PI). If a participant does not receive protocol therapy following registration, the participant's registration on the study must be canceled. Registration cancellations must be made in OnCore as soon as possible.

## 4.2 Registration Process for DF/HCC Institutions

DF/HCC Standard Operating Procedure for Human Subject Research Titled *Subject Protocol Registration* (SOP #: REGIST-101) must be followed.

# 5. TREATMENT PLAN

## 5.1 Treatment Regimen

All patients will receive combination therapy with EGF816 and gefitinib in an open-label fashion. A treatment cycle will be defined as 28 days. After completing 1 year of study treatment, visits will occur every 6 weeks.

The first six patients enrolled in the study will constitute a safety run-in; if severe unexpected toxicities are observed during cycle 1 among these six patients, further expansion cohorts at lower dose levels will be explored. Severe unexpected toxicities will be defined as any grade 3 or higher adverse event assessed to be treatment-related by the treating physician occurring in > 1/6 patients during the safety run-in. Rash will be excluded as grade 3 rash during the 1st cycle has occured with each drug individually and is typically responsive to dose hold. If >1 patient has a grade 3 or higher treatment-related adverse event during cycle 1 of treatment, we will de-escalate treatment to gefitinib 250 mg QD and EGF816 100 mg QD.

EGF816 will be supplied by Novartis to the investigational drug pharmacy at all participating sites. Gefitinib will be supplied directly to the patient through prescription as a commercial product. As stated in the eligibility criteria, only patients with insurance approval to obtain gefitinib or who agree to self-pay for gefitinib will be able to participate in this study. Upon signing of the study ICF and confirmation of eligibility, participants will be prescribed a 30-day (one 28-day cycle; with two additional pills in case of lost, dropped pills) supply of gefitinib. C1D1 will begin only once the supply of gefitinib is in the patient's possession.

All patients will receive gefitinib 250 mg orally once daily and EGF816 100 mg orally once daily without interruption, unless an interruption is required to manage treatment-related toxicity (as outlined in Tables 6-1 and 6-2). Patients will be monitored at the start of each 28-day treatment cycle. Treatment will be administered on an outpatient basis. The participant will be requested to maintain a medication diary of each dose of medication. The medication diary will be returned to clinic staff at the end of each cycle.

Reported adverse events and potential risks are described in Section 7. Appropriate dose modifications are described in Section 6. No investigational or commercial agents or therapies other than those described below may be administered with the intent to treat the participant's malignancy.

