## **1. OBJECTIVES**

## 1.1 Study Design

This is a single arm, open-label phase II study evaluating the safety and efficacy of the combination of the third-generation EGFR inhibitor EGF816 with the first-generation EGFR inhibitor gefitinib in the treatment of TKI-naïve *EGFR*-mutant non-small cell lung cancer. The study will have a Simon two-stage design with eleven patients enrolled in the first stage and a plan to enroll a total of 36 patients (25 patients in the second stage) if at least seven patients remain progression-free at nine months in the first stage. The first six patients enrolled in the study will constitute a safety run-in evaluating the safety of the combination of EGF816 at the recommended phase II dose of 150mg QD and gefitinib at a standard dose of 250mg QD. If unexpected toxicities are observed among the first six patients, expansion cohorts will be added to explore different doses and/or schedules of the combination.

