#### Table 6-10. Guidelines for management of maculopapular rash

CTCAE Grade	Adverse Event Management	Action and Dose
		Modification
Grade 1	Initiate appropriate	Continue both study drugs at
	symptomatic care (Refer to	same dose level
	Table 6-9)	
	Use mild-strength topical	
	steroid (e.g. 1%	
	hydrocortisone cream) on	

	affected areas			
Grade 2	Re-assess after 1 week         Initiate appropriate	Continue both study drugs at		
	symptomatic care (Refer to Table 6-9) Use moderate-strength topical steroid (e.g. 2.5% hydrocortisone cream or 0.5% fluticasone cream) on affected areas PLUS low-dose oral steroid (e.g. 5mg-10mg PO QD for 1 week) with taper	same dose level If no recovery or worsened within 1 week, interrupt EGF816 and gefitinib until recovery to $\leq$ Grade 1. Once rash has recovered to $\leq$ Grade 1, restart EGF816 at one level reduced from the previous dose level  . Drugs should be		
	Re-assess after 1 week	reintroduced one at a time; if no recurrent rash occurs with introduction of EGF816, gefitinib can be resumed at the original dose level.		
Grade ≥ 3	Initiate appropriate symptomatic care (Refer to Table 6-9) Use moderate-strength topical steroid on affected areas PLUS mid-dose oral steroid (e.g. 20- 40mg PO QD for 1 week) with taper over 1-2 weeks or IV steroid (e.g. methylprednisolone 20-30mg IV BID for 3 days) if clinically indicated Consult dermatologist	Interrupt both study drugs until rash recovers to $\leq$ Grade 1. Once recovers to $\leq$ Grade 1, restart EGF816 at one level reduced from the previous dose level. Drugs should be reintroduced one at a time; EGF816 should be resumed first and, if no recurrent rash occurs within a week, gefitinib can be resumed at original dose level. Oral antihistamine therapies (e.g. levocetirizine 5mg QD, desloratadine 5mg QD, or fexofenadine 180 mg QD) should be given concurrently with study drugs for 4 weeks when restarting treatment. If no recovery to $\leq$ Grade 2 within 3 weeks, permanently discontinue EGF816. Gefitinib can be continued. Patients who develop more		
		than 1 episode of Grade $\geq 3$ rash will be permanently discontinued from EGF816.		
1. Maculopapular rash ir	ncludes macular rash, papular ras			

2. For all grades of maculopapular rash, consider skin biopsy for pathologic evaluation.

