#### **Unexpected Adverse Events**

For the purposes of this study, an adverse event is considered unexpected when it varies in nature, intensity or frequency from information provided in the Investigator's Brochure.

• **CTCAE term (AE description) and grade:** The descriptions and grading scales found in the revised NCI Common Terminology Criteria for Adverse Events (CTCAE) version 4.0 will be utilized for AE reporting. All appropriate treatment areas should have access to a copy of the CTCAE version 4.0. A copy of the CTCAE version 4.0 can be downloaded from the CTEP web site http://ctep.cancer.gov/protocolDevelopment/electronic\_applications/ctc.htm.

• For expedited reporting purposes only:

- AEs for the agent(s) that are listed above should be reported only if the adverse event varies in nature, intensity or frequency from the expected toxicity information which is provided.
- Other AEs for the protocol that do not require expedited reporting are outlined in the next section (Expedited Adverse Event Reporting) under the sub-heading of Protocol-Specific Expedited Adverse Event Reporting Exclusions.
- **Attribution** of the AE:
  - Definite The AE is clearly related to the study treatment.
  - Probable The AE *is likely related* to the study treatment.

- Possible The AE may be related to the study treatment.
- Unlikely The AE is doubtfully related to the study treatment.
- Unrelated The AE is clearly NOT related to the study treatment.

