# 12.2 Data Safety Monitoring

The DF/HCC Data and Safety Monitoring Committee (DSMC) will review and monitor toxicity and accrual data from this study. The committee is composed of clinical specialists with experience in oncology and who have no direct relationship with the study. Information that raises any questions about participant safety will be addressed with the Overall PI and study team.

The DSMC will review each protocol up to four times a year or more often if required to review toxicity and accrual data. Information to be provided to the committee may include: up-to-date participant accrual; current dose level information; DLT information; all grade 2 or higher unexpected adverse events that have been reported; summary of all deaths occurring with 30 days of intervention for Phase I or II protocols; for gene therapy protocols, summary of all deaths while being treated and during active follow-up; any response information; audit results, and a summary provided by the study team. Other information (e.g. scans, laboratory values) will be provided upon request.

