# 13.7 Analysis of Secondary Endpoints

Response rate will be assessed as per RECIST, see Section 9.1. Results will be reported with 95% confidence intervals. All patients will be evaluable for response rate. Progression-Free Survival (PFS) will be defined as the duration of time from start of treatment to time of objective disease progression or death. Overall survival (OS) will be defined as the duration of time from start of treatment until death. Analysis will be performed using the Kaplan-Meier method. All patients will be evaluable for survival endpoints.

A summary of the adverse events, grading according to CTCAE and their attributed relatedness to treatment will be provided as a measure of patient safety and tolerability. All patients will be included in the safety analyses.

The first six patients in the study will constitute a safety cohort as outlined in section 5.1. If >1 patient has a grade 3 or higher treatment-related adverse event during cycle 1 of treatment, the dose will be de-escalated as outlined. Six additional patients will be treated at the lower dose to establish safety prior to proceeding to open enrolment of the remainder of the trial. The probability of stopping at the initial dose in order to dose de-escalate and the probability of stopping the trial after the safety run in at the lower dose based on assumptions about the associated underlying toxicity rates are as follows:

True toxicity rate	Probability of reducing the starting dose	Probability of stopping the trial
0.05	0.265	0.033
0.1	0.468	0.114
0.2	0.738	0.345
0.3	0.883	0.580
0.4	0.954	0.767
0.5	0.985	0.890

Biopsies from pre, post and on-treatment will be obtained to facilitate comparative analysis by next-generation sequencing, single-cell RNA sequencing, transcriptional profiling and an evaluation of the emergent resistance mechanisms at the time of progression. Analyses for these outcomes may include the Cox proportional Hazard models for the examination of the relationship between changes in sequencing parameters and time to progression, Sign-Rank test to compare pre and post measurements of gene expression for genes of interest and other correlation tests such as linear regression to examine relationship between relevant outcomes.

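### The run-in trigger excludes rash without a grade limit, although the reason given covers only grade 3 rash, and the de-escalation sentences omit the exclusion

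*Combined protocol and SAP*

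**What the plan says.** Section 5.1 makes the first six patients a safety run-in. It defines severe unexpected toxicity as a related event of grade 3 or higher in more than one of six patients. It then sets rash aside: "Rash will be excluded as grade 3 rash during the" first cycle has occurred with each drug alone and typically responds to holding the dose. The next sentence sets the action, de-escalation to EGF816 100 mg with gefitinib 250 mg, and does not repeat the exclusion.

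Section 13.7 restates the rule, also without the exclusion: "If >1 patient has a grade 3 or higher treatment-related adverse event during cycle 1 of treatment, the dose will be de-escalated as outlined". It refers to section 5.1 for the details and adds: "Six additional patients will be treated at the lower dose to establish safety prior to proceeding to open enrolment".

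Other provisions bear on severe rash:

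- **Section 1.1:** "If unexpected toxicities are observed among the first six patients, expansion cohorts will be added to explore different doses and/or schedules of the combination".
- **Section 7.1:** an event is unexpected "when it varies in nature, intensity or frequency from information provided in the" Investigator's Brochure.
- **Section 12.2:** the material that may go to the safety monitoring committee includes "all grade 2 or higher unexpected adverse events that have been reported".
- **Table 6-10 (maculopapular rash):** one row covers grade 3 and above. After recovery to grade 1 or lower the instruction is to "restart EGF816 at one level reduced from the previous dose level. Drugs should be reintroduced one at a time; EGF816 should be resumed first". If the rash has not come down to grade 2 or lower, the instruction is "within 3 weeks, permanently discontinue EGF816. Gefitinib can be continued".
- **Table 6-11 (other rashes):** there is no grade 4 row. The general dose-modification table in 6.1 stops treatment permanently at grade 4.

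**The concern.** The run-in count is the only rule in the plan that changes the dose for the next patients automatically. Both drugs cause rash, so unusually severe rash is one of the things a run-in of this combination should be able to detect. A reason that speaks of grade 3 rash does not explain why grade 4 rash is left out as well.

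The second difficulty is that the exclusion stands in the definition but in neither de-escalation sentence. Two people applying the plan to the same six patients could count differently. If several patients have severe rash, that would decide whether the dose is reduced.

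**Working it through.** **1. The plan's own figures.** For six patients with true toxicity rate p, the stated rule of more than one event has probability P(X ≥ 2) = 1 − (1 − p)^6 − 6p(1 − p)^5.

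| True rate p | P(X ≥ 2 of 6) | 13.7, stopping the trial |
|---|---|---|
| 0.05 | 0.033 | 0.033 |
| 0.1 | 0.114 | 0.114 |
| 0.2 | 0.345 | 0.345 |
| 0.3 | 0.580 | 0.580 |
| 0.4 | 0.767 | 0.767 |
| 0.5 | 0.891 | 0.890 |

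The column for stopping the trial therefore uses a count of two or more of six. The plan does not state that count in words for the six patients at the lower dose. The other column, for reducing the starting dose, matches one or more of six (for example 1 − 0.95^6 = 0.265). That is a separate matter and is not used here.

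**2. Which rash counts under each reading.**

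| Reading | Grade 3 rash | Grade 4 rash |
|---|---|---|
| A. 5.1 definition as worded; exclusion carried into 13.7 by its reference to 5.1 | not counted | not counted |
| B. Exclusion limited to what its reason covers | not counted | counted |
| C. De-escalation sentences in 5.1 and 13.7 read alone | counted | counted |

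A is the natural reading, because 5.1 places the exclusion directly after the definition. B matches the stated reason. C follows from the operative sentences taken by themselves.

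**3. What the documents allow on size.** Section 2.2.2 gives single-agent EGF816 data on 148 patients: any related grade 3/4 event 29.7%, related grade 3/4 rash 15.5%. So 29.7% − 15.5% = 14.2% had a related grade 3/4 event and no grade 3/4 rash.

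- Reading C, p = 0.297: 1 − 0.703^6 − 6(0.297)(0.703^5) = 1 − 0.121 − 0.306 = 0.573.
- Reading A, p = 0.142, if no patient with rash had another qualifying event: 1 − 0.858^6 − 6(0.142)(0.858^5) = 1 − 0.399 − 0.396 = 0.205. If some did, the figure is higher.
- Reading B lies between. It needs f, the share of grade 3/4 rash that is grade 4, which the documents do not give.

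As an illustration only, take p = 0.142 + 0.155f:

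| Assumed f | p | P(X ≥ 2 of 6) | Rise over reading A |
|---|---|---|---|
| 0 | 0.142 | 0.205 | 0 |
| 10% | 0.1575 | 0.241 | 0.036 |
| 25% | 0.181 | 0.297 | 0.093 |

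The rash dose-limiting toxicities named in 2.2.2 are all grade 3. That is compatible with a small f but does not establish it. The inputs are single-agent, cover all dose levels and are not limited to cycle 1, so they show how the readings differ and do not predict the combination's rates.

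**The case against.** The strongest reply is that the wording is loose but severe rash is well covered. The exclusion sentence names grade 3 rash as its subject, so a reader could already confine it to grade 3. The de-escalation sentences carry no exclusion at all. The patient-level tables act on severe rash, section 1.1 says that cohorts will be added for unexpected toxicity, and the safety committee reviews toxicity data. Table 6-10 itself handles grade 3 and grade 4 maculopapular rash in one row, so the sponsor may regard both as manageable.

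Much of this stands. A reader might infer that grade 4 rash can never trigger de-escalation. The documents do not support that: the text is ambiguous, and the operative sentences read alone would count it. A reader might also infer that patients with severe rash are unprotected, and the tables show otherwise. What the reply leaves is that the patient-level rules do not alter the next patient's dose. The routes through 1.1 and 12.2 depend on judgement, and 5.1 gives its own, narrower definition of severe unexpected toxicity. If the sponsor does mean to leave out grade 4 maculopapular rash, 5.1 should say so.

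A stronger reading is that the exclusion is also wrong for grade 3 rash that does not recover on hold. The documents do not make that an error. A response described as typical already allows exceptions, and the reason applies to grade 3 rash as a class. Counting by recovery has a price too: with the three-week window of Table 6-10, a rash held on day 28 would not be settled until day 28 + 21 = day 49, well after a decision meant to rest on cycle 1.

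**Conclusion.** The point holds, as a minor one. The exclusion is wider than its reason, so on the natural reading related rash of grade 4 or higher does not count toward cohort de-escalation. The de-escalation sentences in 5.1 and 13.7 are inconsistent with the definition.

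The effect on the chance of de-escalation cannot be estimated, because the documents give neither the grade 4 share of severe rash nor any rate for the combination. It is small if grade 4 rash is rare. The values in the illustration depend on an assumed share and are not bounds.

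The practical effect is further limited if the first run-in decision has been made. Sections 5.1 and 5.3.1 and Table 6-1 already give EGF816 100 mg, the de-escalated dose, while 1.1 still gives 150 mg. The documents do not say whether the six further patients in 13.7 have been treated. If they have not, the definition still governs them.

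**What to change.** - **Section 5.1, exclusion:** replace the rash sentence with: *Grade 3 rash will be excluded; grade 4 or higher treatment-related rash will count.*
- **Sections 5.1 and 13.7, de-escalation sentences:** add *excluding grade 3 rash* to each.
- **Section 13.7, lower-dose patients:** state that the same count applies to the six patients treated at the lower dose.

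The cost is a few words in two sections, with no added patients, procedures or waiting time. Compared with the natural reading, de-escalation becomes very slightly more likely if grade 4 rash is rare. The sponsor may in addition choose to count grade 3 rash that does not recover on hold. If so, 5.1 should state the recovery criterion and accept that some decisions will come later.

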## 2.2.2 Clinical Experience

CEGF816X2101 is the first-in-human Phase I/II study of single-agent oral EGF816, and is currently ongoing. As of the data cut-off date (18-Dec-2015), 148 patients have been treated with EGF816 capsules or tablets at seven dose levels: 75 mg q.d. (N=7), 100 mg q.d. (N=29), 150 mg q.d. (N=64), 200 mg q.d. (N=8), 225 mg q.d. (N=24), 300 mg q.d. (N=5) and 350 mg q.d. (N=11). Eighty-four patients (56.8%) were still receiving treatment and 64 patients (43.2%) had discontinued treatment. Of these 64 patients, 53 (35.8%) discontinued treatment due to progressive disease, three (2.0%) discontinued treatment due to AEs, and 3 (2.0%) discontinued treatment due to death. Of the three patients who discontinued treatment due to

AE, one patient at the 350 mg q.d. reported Grade 3 maculopapular rash, one patient at the 150 mg daily dose reported Grade 3 interstitial lung disease, and one patient at the 300 mg daily dose reported Grade 3 pulmonary oedema. Of the three patients who discontinued treatment due to death, one patient died due to sepsis (considered not related to study treatment), one patient died due to hepatitis B virus (HBV) reactivation (considered related to study treatment), and one patient died due to pneumonia (considered not related to study treatment).

As of 18-Dec-2015, dose-limiting toxicities (DLT) were reported in five patients: one patient at the dose level of 150 mg capsule reported Grade 3 maculopapular rash that resulted in temporary treatment interruption, one patient at the dose level of 225 mg capsule reported Grade 3 maculopapular rash that resulted in temporary treatment interruption, one patient at the dose level of 350 mg capsule reported Grade 3 acute kidney failure and Grade 3 maculopapular rash that resulted in temporary treatment at the dose level of 350 mg capsule reported Grade 3 acute kidney failure and Grade 3 maculopapular rash that resulted in temporary treatment at the dose level of 350 mg capsule reported Grade 3 maculopapular rash that resulted in permanent discontinuation of treatment, and one patient at the dose level of 350 mg capsule reported. Grade 3 enteritis and Grade 3 dehydration that resulted in temporary treatment interruption.

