# **13.2** Sample Size, Accrual Rate and Study Duration

As stated above, 11 patients will be enrolled in the first stage of the study, with a planned second stage of 25 patients if at least 7 patients in the first-stage are progression-free at nine months. The null will be rejected and the study deemed positive if at least 23 total patients are progression-free at 9 months.

We expect to accrue approximately 10-15 patients/year, therefore assuming the study advances to the second stage and that there may be a brief pause in enrollment between the first and second stage (to allow for patients to reach the 9 month endpoint), will complete accrual for the study within 3 years. Final data for the primary endpoint will be mature within 4 years.

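### No enrolment hold is stated while the first six run-in patients complete cycle 1, and the written trigger sets no action for a single treatment-related death

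*Combined protocol and SAP*

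**What the plan says.** Section 5.1 defines the run-in by order of enrolment: "The first six patients enrolled in the study will constitute a safety run-in". Severe unexpected toxicity is "any grade 3 or higher adverse event assessed to be treatment-related by the treating physician occurring in > 1/6 patients during the safety run-in", with rash excluded. The action rule follows: "If >1 patient has a grade 3 or higher treatment-related adverse event during cycle 1 of treatment, we will de-escalate". Section 13.7 repeats the count: "If >1 patient has a grade 3 or higher treatment-related adverse event during cycle 1 of treatment, the dose will be de-escalated as outlined". Neither section has a separate line for a Grade 5 event.

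On enrolment, three places matter:

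- Section 13.7 gates the trial after a de-escalation: "Six additional patients will be treated at the lower dose to establish safety prior to proceeding to open enrolment of the remainder of the trial".
- Section 13.2 allows that "there may be a brief pause in enrollment between the first and second stage", so that patients can reach the nine-month endpoint.
- Section 4.1 lets participants start therapy once registered, with no cohort-release step.

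Section 13.5 gives the interim monitoring plan as not applicable. Section 12.2 has the DSMC review toxicity and accrual up to four times a year, or more often if required. Section 5.5 requires immediate notice to the Overall PI of life-threatening complications, and Sections 7.2 and 7.3 cover SAE reporting to the PI, IRB, manufacturer and FDA.

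**The concern.** A run-in protects later patients only if they wait for its result. Toxicity is read over 28 days, so there is a window after the sixth patient starts in which the result is not yet known. Nothing written stops a seventh patient from starting treatment in that window. That patient would be in the safety analysis, which covers all patients, but would belong to neither six-patient cohort on which the decision rests.

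The trigger also counts patients without regard to severity beyond Grade 3. One related death among six counts the same as one related Grade 3 laboratory abnormality, and neither reaches more than one patient. Section 6 acknowledges that the two drugs have overlapping toxicities. Section 2.2.2 reports that, on single-agent EGF816, "one patient died due to hepatitis B virus (HBV) reactivation (considered related to study treatment". The reporting routes would make a death in the run-in known quickly, but none of them carries a pre-set effect on accrual.

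**Working it through.** **1. The plan's own table.** Section 13.7 tabulates the run-in's operating characteristics. With X ~ Binomial(6, p), P(X ≥ 1) = 1 − (1−p)^6 and P(X ≥ 2) = 1 − (1−p)^6 − 6p(1−p)^5.

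| True toxicity p | Table: reduce dose | P(X ≥ 1) | Table: stop trial | P(X ≥ 2) |
|---|---|---|---|---|
| 0.05 | 0.265 | 0.265 | 0.033 | 0.033 |
| 0.1 | 0.468 | 0.469 | 0.114 | 0.114 |
| 0.2 | 0.738 | 0.738 | 0.345 | 0.345 |
| 0.3 | 0.883 | 0.882 | 0.580 | 0.580 |
| 0.4 | 0.954 | 0.953 | 0.767 | 0.767 |
| 0.5 | 0.985 | 0.984 | 0.890 | 0.891 |

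The column headed "Probability of reducing the starting dose" is therefore the chance of at least one event in six, to within 0.001. The trial-stopping column is the chance of at least two. The text makes at least two the condition for reduction. Text and table disagree whenever exactly one of six patients has an event. That has probability 0.354 at p = 0.1 and 0.393 at p = 0.2.

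**2. Entries while cycle 1 is unread.** Inputs: 10-15 patients a year (Section 13.2) and a 28-day cycle (Section 5.1). With Poisson arrivals the mean is rate × 28/365.

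- 10 a year: 10 × 28/365 = 0.77; P(at least one) = 1 − exp(−0.767) = 0.54.
- 15 a year: 15 × 28/365 = 1.15; P(at least one) = 1 − exp(−1.151) = 0.68.

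**3. Entries followed by the written trigger.** Treating arrivals as independent of toxicity, multiply by P(X ≥ 2):

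- p = 0.1: 0.536 × 0.114 = 0.061 and 0.684 × 0.114 = 0.078, or 6-8%.
- p = 0.2: 0.536 × 0.345 = 0.185 and 0.684 × 0.345 = 0.236, or 18-24%.

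**4. One death in six.** The documents give no death rate for the combination. The only documented anchor is one related death among 148 single-agent patients (Section 2.2.2), or 0.7%. An upper value of 5% is assumed. P(exactly one of six) = 6q(1−q)^5.

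- q = 1/148: 6 × 0.00676 × 0.9667 = 0.04.
- q = 0.05: 6 × 0.05 × 0.7738 = 0.23.

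**5. Would other events fire the trigger anyway?** Non-fatal Grade 3 or higher events in other patients also count. If deaths (rate q) are a subset of all counted toxicities (rate p), then P(trigger not fired, given at least one death) = 6q(1−p)^5 / [1 − (1−q)^6].

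| Death rate q | p = 0.1 | p = 0.2 |
|---|---|---|
| 1/148 | 0.60 | 0.33 |
| 0.02 (assumed) | 0.62 | 0.34 |
| 0.05 (assumed) | 0.67 | 0.37 |

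A run-in that includes a death would leave the written trigger unfired in about 60-67% of cases at 10% toxicity and 33-37% at 20%.

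**The case against.** The best defence is that a gate is implied. Section 13.7 places the second cohort ahead of open enrolment and speaks of stopping at the initial dose, which suggests that enrolment is not open during the first cohort either. A reader might go further the other way and infer that the run-in never holds enrolment. That is not supported, because the de-escalated cohort is expressly gated. What stands is narrower: the stated gate applies only once the trigger has fired, and it does not cover the weeks when the first six are still being read.

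A reader might also infer that a single death leaves the dose unchanged. The documents do not support that as a flat statement. It follows from the text, but under the Section 13.7 table one event of any severity reduces the dose. Nor is it settled that later patients would enter at a dose above the fallback. Section 1.1 gives 150 mg of EGF816 for the run-in, whereas Sections 5.1 and 5.3.1 and Table 6-1 give 100 mg, which is also the dose that Section 5.1 names for de-escalation.

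Finally, it can be said that oversight is ample and the exposure small. Both are fair. The PI or DSMC could halt accrual at any time, about one patient is involved, and the one related death was HBV reactivation, for which this protocol requires screening and antiviral measures. That limits the size of the point. Discretion is still not a pre-set rule.

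**Conclusion.** The point holds in limited form. The protocol states no enrolment hold for the first six patients, and its written trigger sets no action for a single related death. About one patient (0.77 to 1.15) would be expected to enter during the open window. The chance that someone enters and the written trigger then fires is 6-8% at 10% true toxicity and 18-24% at 20%. Exactly one related death in six has probability 0.04 at the single-agent rate and 0.23 at an assumed 5%.

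These figures rest on Poisson accrual at the stated rate, independence of accrual and toxicity, and the more-than-one rule as written. The toxicity rates are illustrative, and the death rates are either assumed or carried over from single-agent data with longer follow-up than one cycle.

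The documents do not show that patients would be exposed to a dose known to be excessive, or that a death would go unreviewed. This is an inexpensive improvement that should be made. It leaves the efficacy design untouched.

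**What to change.** Add two sentences to Sections 5.1 and 13.7:

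1. *Enrolment is held after the sixth patient of each run-in cohort until all six have completed cycle 1, or have left treatment before its end, and the decision is recorded.*
2. *Any treatment-related Grade 5 event in a run-in cohort pauses enrolment pending DSMC review, whatever the count.*

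Both concern enrolment and oversight; neither sets a dose or a rule for managing a patient.

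Separately, the sponsor should reconcile two contradictions that determine what the run-in does. The first is the more-than-one text against the table, which encodes at least one of six for reduction and at least two for stopping. The second is 150 mg in Section 1.1 against 100 mg in Sections 5.1 and 5.3.1 and Table 6-1. This review takes no position on which is right. The table should then be recalculated for the rule adopted.

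The cost is up to 28 days without accrual per cohort, deferring roughly one patient, and a rare ad hoc DSMC review.
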